RESEARCH PROTOCOL OUTLINE

Instructions: Protocols should be formatted according to the following outline and include all of the elements indicated.

Title of Project: Quality Control: A prospective analysis of external ventricular drain effectiveness.

Principal Investigator: [name], Department of Neurosurgery

Abstract

In an effort to decrease the number of external ventricular drain (EVD) catheter related infections, this research will compare the efficacy of the standard EVD catheters utilized by Oklahoma University Medical Center (OUMC). These catheters will be compared in three principle areas: 1) incidence of infection, 2) cost analysis, and 3) average durations of placement, without deviation from existing standard of care (SOC). The three EVD catheters being compared in this study are 1) the Integra External Drainage Catheter (non-impregnated), 2) the Ventriclear EVD Antibiotic Catheters (antibiotic-impregnated), and 3) Codman Bactiseal EVD Catheter Set (antibiotic-impregnated). The goal of this prospective study is to determine whether the use of antibiotic impregnated EVDs vs non-impregnated EVDs will result in lower infection rates.

A. Specific Aims

The hypothesis for this research study is that antibiotic impregnated EVDs are more effective in reducing the number of EVD catheter related infections. The long-term objective is a reduction in the number of EVD catheter related infections.

B. Background and Significance

While use of sterile techniques and periprocedural antibiotics have traditionally been used to combat infection, infection rates remain above goal, leading to the question of whether the antibiotic impregnated catheter should be added to the standard of care. With the knowledge gained, we hope to decrease the amount of EVD catheter related infections and reduce use of prolonged antibiotics.

C. Preliminary Studies/Progress Report

D. Research Design and Methods

All patients, both male and female, ages 18-75, requiring EVD placement will be solicited for enrollment into this study, except those who are incarcerated and/or

may be pregnant. The indications for EVD placement are 1) increased intracranial pressure, 2) hydrocephalus, 3) interventricular hemorrhage, and 4) subarachnoid hemorrhage with poor clinical exam. Upon receipt of informed consent, participants will be randomly assigned to receive one of the three EVDs being studied. The EVDs being studied are 1) the Integra External Drainage Catheter, 2) the Ventriclear EVD Antibiotic Catheter, and 3) Codman Bactiseal EVD Catheter Set. A random number generator will be utilized to randomly assign participants to one of three EVDs. Study data will be collected from patient's electronic medical record (EMR) both at OU Medical Center and OU Physicians. Study data will include participant information, infection outcomes, equipment cost, and duration of placement will be added to a secure database for later analysis. The study will enroll a total of 252 participants, after which study enrollment will be closed. The database will be maintained by the Project Contact: [name], M-HR. Patients who require placement of an EVD are, by nature of their condition (which includes altered mental status), unable to consent for the procedure. As such, a Legally Authorized Representative (LAR) must consent for the procedure on behalf of the patient. The LAR is either the patient's next of kin, or if available, the designee on the patient's living will, power of attorney, or advance directive. The same LAR will be asked to consent for this study, on behalf of the patient.

E. Statistical Methods

The statistical method for this study will be a one-way ANOVA. Utilizing G*Power 3.1.9.2 software, a priori power analysis provided the following results:

[1] -- Friday, December 12, 2014 -- 10:25:39

F tests – ANOVA: Fixed effects, omnibus, one-way

[figure not shown]
Analysis: A priori: Compute required sample size

Input:

Effect size f	= 0.25
α err prob	= 0.05
Power (1- β err prob)	= 0.95
Number of groups	= 3

Output:

Noncentrality parameter λ	= 15.7500000
Critical F	= 3.0320649
Numerator df	= 2
Denominator df	= 249
Total sample size	= 252
Actual power	= 0.9514888

F. Gender/Minority/Pediatric Inclusion for Research

This project will include both men and women age 18-75.

G. Human Participants

1. This project will recruit 252 participants, age 18-75, who require placement of an external ventricular drain. All adult patients who require an EVD will be included.
2. Research material will consist of records and data.
3. Recruitment will take place at the bedside or within a consultation room in the OUMC and will be administered by the assigned resident. The bedside is frequently within the emergency department, intensive care unit, or step down care unit. Recruitment of non-English speaking participants will be done via a translator. Given that there is no deviation from the existing standard of care, participant coercion is not a significant concern.
4. This research does not involve more than minimal risk to the patient.
5. Patient records, including PHI, will be stored in a secure database on a secure network that is password protected. Access to this database will only be granted to essential personnel.
6. While use of sterile techniques and periprocedural antibiotics have traditionally been used to combat infection, infection rates remain above goal, leading to the question of whether the antibiotic impregnated catheter should be added to the standard of care. With the knowledge gained, we hope to decrease the amount of EVD catheter related infections and reduce use of prolonged antibiotics.
7. The three EVD catheters being studies are part of the existing standard of care at OUMC and therefore do not produce any additional risk to the patient.

H. Data and Safety Monitoring Plan

1. All electronic data will be maintained in a password protected database on a secure server. All non-electronic data (i.e. consent form) will be stored in a locked file cabinet in the Project Contact's office.
 - a. Should any type of breach occur, this will be immediately reported to the IRB and study PI.
2. The study Principal Investigator will be responsible for monitoring the study.
3. Additionally, [name], Neurologist, will monitor study data.

I. Literature Cited

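### Does comparing mean drain duration require reasons for removal, infection dates and an infection rate per catheter-day?

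*Combined protocol and SAP*

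**What the plan says.** The Abstract names three areas of comparison: "These catheters will be compared in three principle areas: 1) incidence of infection, 2) cost analysis, and 3) average durations of placement". It gives the goal as learning "whether the use of antibiotic impregnated EVDs vs non-impregnated EVDs will result in lower infection rates", and Section A states the hypothesis that "antibiotic impregnated EVDs are more effective in reducing the number of EVD catheter related infections".

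Section D sets out the data in broad categories: "Study data will include participant information, infection outcomes, equipment cost, and duration of placement". The source is the "electronic medical record (EMR) both at OU Medical Center and OU Physicians". The categories are not broken down. Reason for removal and date of infection are not named, although a date could fall under infection outcomes. Duration has no stated end-point, and neither a longer nor a shorter placement is called favourable.

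Section E names one method: "The statistical method for this study will be a one-way ANOVA". No analysis adjusts for time at risk.

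**The concern.** A drain can come out because the patient recovers, becomes infected or dies, or because the device fails. (The documents do not list these reasons; they are assumed here. One indication in Section D, "subarachnoid hemorrhage with poor clinical exam", makes some deaths with a drain in place plausible.) If all endings are pooled into one mean, its direction is ambiguous. A catheter that prevents infection avoids some early removals and so lengthens mean duration, but slower recovery lengthens it too.

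There is a companion worry about infection. Incidence per patient combines the daily risk with the number of days at risk. If one catheter stayed in longer, a lower daily risk could be partly hidden.

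At stake would be the reading of one of the three named comparisons and, if durations differed greatly, the size of the apparent infection effect. The natural remedy would be to extract the reason for removal and the infection date, and to add infections per 1,000 catheter-days as a supportive analysis.

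**Working it through.** **The plan's own figure.** Section E gives f = 0.25, alpha 0.05, three groups and N = 252. The noncentrality is 0.25² × 252 = 15.75; with 2 and 249 degrees of freedom the critical F is 3.0321 and the power 0.9515, as printed. N = 249 gives 0.9491, so 252 is the smallest equal-arm total that reaches 0.95. Nothing in this point alters that figure. Equal allocation is assumed below: 252 / 3 = 84 per arm.

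**Assumed inputs.** The documents give no infection, death or removal rates. For illustration, take constant daily rates in the reference arm of i = 0.012 (infection), d = 0.02 (death) and r = 0.10 (other removal), with placement ending at infection. Then

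- infection proportion = i / (i + d + r)
- mean duration = 1 / (i + d + r)
- risk ratio = daily rate ratio × ratio of mean durations.

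**Is mean duration ambiguous?**

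| Scenario | i, d, r | Infection | Mean duration |
|---|---|---|---|
| Reference | 0.012, 0.02, 0.10 | 0.012/0.132 = 9.1% | 1/0.132 = 7.58 days |
| Infection halved | 0.006, 0.02, 0.10 | 0.006/0.126 = 4.8% | 1/0.126 = 7.94 days |
| Slower other removal | 0.012, 0.02, 0.094 | 0.012/0.126 = 9.5% | 1/0.126 = 7.94 days |

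Yes: the last two rows share a mean. But their ratio to the reference is 7.94/7.58 = 1.048. In simulated trials (exponential durations, 84 per arm, one reference arm against two identical arms) the planned ANOVA of duration rejects about 5.7% of the time at that ratio, barely above its 5% false-positive rate. The ambiguity concerns a difference that this trial would rarely report.

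**Is the infection comparison distorted?** A true daily rate ratio of 0.50 appears as follows:

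| Ratio of mean durations | Risk ratio | ANOVA of duration rejects |
|---|---|---|
| 1.048 | 0.50 × 1.048 = 0.524 | 5.7% |
| 1.10 | 0.55 | 9% |
| 1.25 | 0.625 | 27% |
| 1.50 | 0.75 | 74% |
| 2.00 | 1.00 | over 99% |

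The distortion is small unless durations differ a great deal, and the planned analysis usually flags differences of 50% or more. With less spread in duration (gamma, shape 2), a 25% difference is flagged about 51% of the time.

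**Can the planned summaries give the rate?** Divide incidence by mean duration, allowing k further days of drainage after infection: rate = proportion / (mean + proportion × k).

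- k = 0: 12.0 and 6.0 per 1,000 days, ratio 0.50.
- k = 7: 0.0909/8.21 = 11.07 and 0.0476/8.27 = 5.76, ratio 0.52.
- k = 14: 0.0909/8.85 = 10.27 and 0.0476/8.60 = 5.54, ratio 0.54.

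**Would a formal rate be more precise?** Expected infections are 84 × 0.0909 = 7.64 and 84 × 0.0476 = 4.0 per arm (8.0 with the two impregnated arms pooled).

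- Rate ratio: 0.50 × exp(±1.96 × √(1/7.64 + 1/4.0)) = 0.15 to 1.68; pooled, 0.19 to 1.35.
- Risk ratio: 0.524 × exp(±1.96 × √(1/7.64 − 1/84 + 1/4.0 − 1/84)) = 0.16 to 1.69; pooled, 0.20 to 1.36.

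The intervals are practically the same. A shift from 0.50 to 0.54 cannot be seen inside either.

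**Would removal reasons be informative?** A reason recorded for 15% of an arm has a 95% half-width of 1.96 × √(0.15 × 0.85/84) = 7.6 percentage points; a difference between two arms has 10.8. They could only be descriptive.

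**The case for a change.** The strongest case for acting is that the sponsor chose duration as a headline comparison and would publish it without the field that explains it. On the assumed rates, about 91% of placements (0.120/0.132) end for reasons other than infection, and nothing listed separates recovery from malfunction or death. Nor can the infection result be relied on to settle which explanation holds: telling 4.8% from 9.1% has only about 18% to 20% power with 84 against 84, and about 28% with the impregnated arms pooled. Incidence divided by mean duration also comes without an interval or a stated end of time at risk. The cost is at most five extra fields and a few lines in Section E.

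Part of this stands. Mean duration alone cannot show why drains were removed, and a reason for removal would help a reader. The catheter-day rate, however, bears on the infection result and not on duration, so it does not serve the purpose for which it would be added. Its denominator accrues after randomisation. It would also need rules for infections found after removal and for replaced catheters, and a definition of infection that the documents do not give. The records it would draw on are already being read ("Study data will be collected from patient's electronic medical record (EMR) both at OU Medical Center and OU Physicians"), and duration ordinarily requires the placement and removal dates. An analyst who meets an unexpected difference in duration can probably go back for the reasons.

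**Conclusion.** No change is needed. The plan promises a comparison of average duration by arm and attaches no benefit or harm to either direction. As a description of randomised groups, that comparison is valid. The per-patient infection comparison answers the aim of fewer infections without bias from this gap and should stay the main one.

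The additions would gain little: a rate ratio already approximated to within 0.50 to 0.54 by two planned summaries, with an interval (0.15 to 1.68) no tighter than that of the plain risk ratio (0.16 to 1.69). Sample size, power and every stated figure are unaffected. Extracting the reason for removal and the infection date, and describing reasons by arm beside mean duration, is a sensible option for the study team.

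The sizes rest on assumed constant daily rates of 1.2%, 2% and 10% and on equal arms. The conclusion would weaken if one catheter lengthened placement by 25% or more. The documents give no reason to expect that, and a difference of 50% or more would usually show in the planned comparison. Whether a one-way ANOVA suits a yes/no infection outcome is a separate and larger question, which this point does not touch.

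### The plan does not say who makes the random draw, whether it is hidden from the recruiting resident, or whether it is final; adjusting for indication is a smaller, optional gain

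*Combined protocol and SAP*

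**What the plan says.** Section D describes allocation in two sentences: "Upon receipt of informed consent, participants will be randomly assigned to receive one of the three EVDs being studied", and "A random number generator will be utilized to randomly assign participants to one of three EVDs". Consent comes from a legally authorized representative (LAR): "The same LAR will be asked to consent for this study, on behalf of the patient". The same section fixes the size: "The study will enroll a total of 252 participants, after which study enrollment will be closed".

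Section G item 3 says who recruits and where: "Recruitment will take place at the bedside or within a consultation room in the OUMC and will be administered by the assigned resident". It adds: "The bedside is frequently within the emergency department, intensive care unit, or step down care unit".

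On indication, Section D states: "The indications for EVD placement are 1) increased intracranial pressure, 2) hydrocephalus, 3) interventricular hemorrhage, and 4) subarachnoid hemorrhage with poor clinical exam". Section E states: "The statistical method for this study will be a one-way ANOVA". Its power output has 3 groups with 2 and 249 degrees of freedom.

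The documents do not state:
- who generates, runs or holds the draw;
- whether the recruiter is kept from it;
- whether each draw is logged and final;
- the allocation ratio;
- any blinding.

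**The concern.** Randomisation is what protects the infection comparison. It does so only if the person deciding whether and how to enrol a patient cannot foresee or change the assignment. The setting puts some strain on this. Recruitment is often urgent and at the bedside, all three catheters are already in use at the centre (Section G item 7), and the stated hypothesis favours the impregnated ones (Section A).

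If a draw could be repeated when the result was unwelcome, patients would differ by catheter in ways that a one-way ANOVA cannot remove. Adjusting for indication would remove the bias only if the steering followed indication alone. Concealment also cannot be restored once patients are enrolled.

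A separate and lesser matter is that indication is known before placement but is not in the planned model. What is at stake there is a little precision, not bias.

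**Working it through.** **1. The plan's own figure.** Inputs from Section E: f = 0.25, alpha = 0.05, 3 groups, N = 252.

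- Noncentrality: f² × N = 0.0625 × 252 = 15.75.
- Critical F with 2 and 249 df: 3.0321.
- Power from the noncentral F distribution: 0.9515. At N = 249 it is 0.9491, so 252 is the smallest equal-arm total that reaches 0.95.

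The stated figures reproduce. The denominator df (252 − 3 = 249) show that catheter is the only factor. Equal arms of 252/3 = 84 are implied by this calculation but not stated. Drawing each catheter with probability 1/3, with no restriction on arm sizes, gives average power 0.950 in simulation, so exact balance is not needed.

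**2. What a non-final draw could do.** Every input here is assumed, because the documents give no infection rates, indication shares or redraw frequency.

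- A share h of patients is at higher risk: 0.1, 0.3 or 0.5.
- Their infection risk is RR times that of the others: 2, 3 or 5.
- When such a patient draws the non-impregnated catheter, the number is redrawn once with probability q.

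Formulas:

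- P(non-impregnated | higher risk): pC = (1/3)(1 − q + q/3). Each antibiotic arm: pO = (1 − pC)/2.
- Higher-risk share in each arm: hC = h·pC / [h·pC + (1 − h)/3], and hO likewise with pO.
- Distortion of the risk ratio: [1 + hO(RR − 1)] / [1 + hC(RR − 1)].

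Worked case, h = 0.3, RR = 3, q = 0.5:

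- pC = (1/3)(0.5 + 0.1667) = 0.2222; pO = 0.3889.
- hC = 0.0667/(0.0667 + 0.2333) = 0.222; hO = 0.1167/(0.1167 + 0.2333) = 0.333.
- Distortion = 1.667/1.444 = 1.154, so a true 0.50 appears as 0.577.
- Number of redraws: 252 × 0.3 × (1/3) × 0.5 = 12.6, about 13.

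Over all nine combinations of h and RR:

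| Redraw probability q | Distortion | True 0.50 appears as |
|---|---|---|
| 0.25 | 1.021–1.105 | 0.51–0.55 |
| 0.50 | 1.043–1.235 | 0.52–0.62 |
| 1.00 | 1.090–1.643 | 0.55–0.82 |

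Steering in the opposite direction would exaggerate the benefit instead.

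**3. False positives with no catheter effect.** Simulated one-way ANOVA, half the patients at higher risk (assumed):

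| Infection risk, lower vs higher | Redraw 50% | Redraw 100% |
|---|---|---|
| 5% vs 15% | 5.4% | 7.3% |
| 5% vs 20% | 5.9% | 10.5% |

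Marked inflation appears only when redraws are systematic.

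**4. Adding indication.** Four indications use three extra parameters, so the df are 2 and 246 and the noncentrality is 15.75/(1 − R²), where R² is the share of variance explained (assumed).

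| R² | Power |
|---|---|
| 0 | 0.9515 |
| 0.01 | 0.9534 |
| 0.03 | 0.9571 |
| 0.05 | 0.9607 |

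The largest gain is 0.9607 − 0.9515 = 0.0092, about 0.01.

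**The case against.** The strongest reply is that the plan already assigns by a generator after consent, and that nothing in it gives the resident any part in the draw. A reader might infer that the resident controls the draw or can read a list in advance. The documents do not support that: they give the resident recruitment only and mention no list. Sections D and G also intend every eligible patient to be approached, which limits discretion over who is asked. A proper procedure may exist and simply be unwritten. All of this stands, and it makes the point an omission rather than a demonstrated flaw. None of it says that the draw is concealed or final, and approaching everyone does not prevent a redraw.

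It is also fair that every bias figure is assumed, that the upper range needs every relevant draw to be repeated, and that false-positive rates stay near 5% when redraws are occasional.

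On indication, a reader might infer that leaving it out biases the comparison. It does not: an unadjusted analysis of a properly randomised trial is valid. Nor do the documents show that indication predicts infection. Adjustment is therefore optional, and it cannot replace concealment. The listed indications are also not said to be mutually exclusive, so using them needs a classification rule.

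**Conclusion.** The point holds as a gap in the written procedure that should be closed before enrolment. The documents leave unstated who draws, whether the recruiter is kept from the result, and whether the result is final. Post-consent assignment protects in part.

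The size of any bias cannot be taken from the documents. Under the assumptions shown, occasional redraws move a true risk ratio of 0.50 only slightly (0.51 to 0.55 at 25%), while systematic redraws could move it to 0.55 to 0.82. Confidence is medium, because actual practice may be better than the text.

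The indication covariate is a secondary improvement worth at most about 0.01 in power for an assumed R² of up to 5%. The plan's sample size and power arithmetic are unaffected.

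**What to change.** **Main change (Section D).** Before enrolment, have someone other than the recruiting resident generate and hold the assignments, with equal probability of each catheter. Exactly 84 per arm is not required. Sequentially numbered, opaque, sealed envelopes are one workable form. Release each assignment once, with a time-stamped log, only after LAR consent is recorded, and allow no redraws. State whether anyone is blinded.

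**Secondary change (Sections D and E).** Record the main indication before release, with a rule for patients who have more than one, and name it as a prespecified covariate in the infection analysis. This is ANCOVA if the ANOVA is kept. If a binary model replaces it, a Firth-penalised logistic fit would suit: at an assumed 5% to 15% infection, 252 patients give about 13 to 38 events, or 2.5 to 7.6 for each of five parameters (two for catheter, three for indication).

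**Cost.** A one-time preparation of the assignments, a log, a few sentences of text, and a short release step at emergency placements. The documents do not say that the Project Contact can be reached at all hours, so envelopes opened with a second staff member present may be easier than release through the database. The indication covariate adds a classification rule to apply at the bedside.

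### Does the lack of a rule for CNS infection already present at catheter insertion undermine the infection comparison?

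*Combined protocol and SAP*

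**What the plan says.** The Abstract sets the comparison: "These catheters will be compared in three principle areas: 1) incidence of infection, 2) cost analysis, and 3) average durations of placement". Its stated goal is "to determine whether the use of antibiotic impregnated EVDs vs non-impregnated EVDs will result in lower infection rates". Section A (Specific Aims) gives the hypothesis that "antibiotic impregnated EVDs are more effective in reducing the number of EVD catheter related infections", and section G, item 6 repeats the target: "we hope to decrease the amount of EVD catheter related infections and reduce use of prolonged antibiotics".

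Section D describes the data: "Study data will include participant information, infection outcomes, equipment cost, and duration of placement". These come from the "electronic medical record (EMR) both at OU Medical Center and OU Physicians". Neither section D nor any other section says what counts as an infection event, or how an infection present before insertion is classified.

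On eligibility, section D says that patients aged 18-75 needing a drain "will be solicited for enrollment into this study, except those who are incarcerated and/or" possibly pregnant. Section G, item 1 adds: "All adult patients who require an EVD will be included". Section D lists four indications: raised intracranial pressure, hydrocephalus, intraventricular haemorrhage, and subarachnoid haemorrhage with a poor examination. CNS infection is not on the list, but the first two indications carry no stated cause.

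**The concern.** The goal and the data item speak of infection without qualification. Nothing stops a patient with meningitis or ventriculitis from being randomised under raised pressure or hydrocephalus. That patient's record will show an infection whichever catheter is used, and the person extracting the data has no written instruction to set it aside. Infection status before insertion is not a named data item either.

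An infection that was there before the catheter cannot be prevented by it. Counting it adds a similar background to each arm, which dilutes the relative effect and costs power on the outcome that carries the hypothesis.

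**Working it through.** **1. The plan's own figure.** Section E gives f = 0.25, alpha 0.05, three groups and N = 252. The noncentrality is 252 × 0.25² = 15.75, the critical F(2, 249) is 3.0321, and the noncentral F distribution gives power 0.9515. All three agree with section E. The point examined here disputes none of these figures.

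**2. Inputs for the check.**
- From section E: the omnibus one-way F test, 252 patients, three groups.
- Assumed: equal allocation (252 / 3 = 84 per arm), since no ratio is stated.
- Assumed: true new-infection risks p of 10/3/3% or 15/5/5% (plain catheter first).
- Assumed: the share q of patients already infected at insertion, varied from 0 to 5%.
- Assumed: a pre-infected patient has no further new event, and prior infection is classified the same way in every arm.

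**3. Formulas.** The observed event rate in an arm is
- q + (1 − q)p if every prior infection is counted;
- 0.5q + (1 − q)p if half are recognised and left out;
- (1 − q)p if none is counted.

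All randomised patients stay in the denominator. Power is the exact probability that F exceeds 3.0321, summed over all outcomes of three independent binomials of size 84.

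**4. Worked case, 10/3/3% at q = 2%.** All counted: 0.02 + 0.98 × 0.10 = 0.1180 and 0.02 + 0.98 × 0.03 = 0.0494, so the risk ratio is 0.0494 / 0.1180 = 0.42. None counted: 0.0980 and 0.0294, so the risk ratio is 0.30. The risk difference is 6.86 points either way, because q cancels: (1 − q)(0.10 − 0.03) = 0.98 × 0.07.

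**5. Power of the planned test.**

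| q (patients of 252) | 10/3/3%: all / half / none counted | RR, all counted | 15/5/5%: all / half / none counted |
|---|---|---|---|
| 0 | 52% | 0.30 | 64% |
| 0.5% (about 1) | 48 / 50 / 52% | 0.33 | 62 / 63 / 64% |
| 1% (2-3) | 45 / 48 / 52% | 0.36 | 59 / 62 / 64% |
| 2% (about 5) | 39 / 44 / 51% | 0.42 | 55 / 59 / 63% |
| 5% (about 13) | 28 / 35 / 50% | 0.54 | 45 / 51 / 62% |

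**6. False positives.** With equal true risks of 5% or 10% in all arms, and prior infections counted at q = 0, 2% or 5%, the rejection rate runs from 4.7% to 5.1%.

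**7. What belongs to this point.** The 10/3/3% and 15/5/5% scenarios correspond to f of about 0.15 and 0.17, not the planned 0.25. The drop from 95% to 52% or 64% in the q = 0 row comes from that difference and has nothing to do with prior infection. Only the movement down each column does.

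**8. Which column the plan points to.** The hypothesis, the long-term objective and section G, item 6 all name infection related to the drain, and the Abstract compares incidence. Both terms require onset after insertion, which is the none-counted case. There the loss at q = 5% is about 2 points in either scenario, and the risk ratio does not move.

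**The case for a change.** The best argument for acting is that an intention is not an event rule. Someone reading a routine record sees an infection and must decide, case by case, whether it belongs to the catheter. One sentence and one yes/no item would settle this before outcomes are read, without touching eligibility, treatment or sample size. The cost is close to nil, and even with half of prior infections recognised some power is kept (44% against 39% at q = 2%, 10/3/3%). All of that is true, and the sentence would do no harm. It does not show that the plan as written leads to a wrong answer: the loss requires a reader to count against the stated target, and nothing in the protocol suggests that.

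A second argument is that the gap is wider: there are no diagnostic criteria, no end to the at-risk window, no unit of analysis and no named assessor. That is correct as a description, but it is a different question. A rule on prior infection would supply none of those things.

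A third is that no blinded assessment is stated, so prior infection could be classified differently by arm. This limits the statement that no arm is favoured: it holds only if classification is alike across arms. Randomisation balances prior infection in expectation; it does not guarantee even-handed reading of records. The documents give no sign of uneven reading, and any figure for it would rest on invented error rates.

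**Conclusion.** No change is needed. The protocol is silent on infection present at insertion, but its target (catheter-related infection, compared by incidence) already excludes it, and an analyst applying that target fills the gap sensibly. On that reading power falls by at most about 2 points, even with 5% of patients infected on arrival. If the target were ignored and every prior infection counted alike in all arms, the loss would be 2 to 4 points at a 0.5% share and 9 to 13 points at 2%. The risk ratio would be pulled toward 1, the risk difference would hardly move, and the false-positive rate would stay near 5%.

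These sizes rest on assumed infection rates, an assumed pre-infected share, equal allocation and even classification across arms. The documents give none of these. The indications list does not name CNS infection, which suggests that such patients would be few but does not rule them out. The conclusion covers the handling of prior infection only; it does not say that the endpoint is otherwise fully defined.

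### Section E gives infection, in effect a yes/no outcome, no method but a one-way ANOVA; the planned F test holds up, but an interval for the catheter difference built on it would be too narrow

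*Combined protocol and SAP*

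**What the plan says.** Section E (Statistical Methods) states: "The statistical method for this study will be a one-way ANOVA". No other method appears anywhere in the document. The power output that follows is for "F tests – ANOVA: Fixed effects, omnibus, one-way", with "Effect size f = 0.25", "α err prob = 0.05" and "Power (1- β err prob) = 0.95", giving a total of 252.

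The Abstract lists three outcomes: "These catheters will be compared in three principle areas: 1) incidence of infection, 2) cost analysis, and 3) average durations of placement". It then gives the goal, which is to "determine whether the use of antibiotic impregnated EVDs vs non-impregnated EVDs will result in lower infection rates". The hypothesis in Section A is also about infections.

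No method is assigned to any one outcome. The document names no contrast, pairwise comparison, confidence interval or multiplicity adjustment, and it assumes no infection rate. Infection is never formally defined as yes/no per patient, but that is the natural reading of an incidence.

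**The concern.** ANOVA estimates one residual variance and uses it for every arm. A yes/no outcome with rate p has variance p(1−p), so the arms have different variances exactly when their infection rates differ, which is what the trial hopes to show.

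The omnibus F test asks only whether the three arms are all alike. It gives neither direction nor size, so it cannot by itself answer whether impregnated catheters lower the infection rate, or by how much. Someone will have to add a contrast or a comparison. With ANOVA the only named method, the default is to build it on the pooled error. The resulting interval would then be the figure used to decide whether impregnated catheters join routine care.

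**Working it through.** **Inputs.** From Section E: three groups, N = 252, alpha 0.05, f = 0.25. Assumed, because the document gives neither: equal allocation (84 per arm) and the infection rates, written as Integra / Ventriclear / Bactiseal.

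**The plan's own figure.** λ = f²N = 0.0625 × 252 = 15.75. With 2 and 249 degrees of freedom the critical F is 3.0321 and the power 0.9515, as stated.

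**The omnibus test.** With 0/1 data the Pearson statistic is a function of F: X² = 252 × 2F / (249 + 2F). At F = 3.0321 this is 5.9913, against a chi-square critical value of 5.9915. The two tests rejected at the same rate in every simulated scenario. Exact size of the F test for common rates of 1% to 20% is 3.1% to 5.1%.

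**The interval for impregnated minus non-impregnated (168 versus 84).**
- ANOVA standard error: √[MSE × (1/84 + 1/168)] = √(MSE × 0.017857).
- True standard error when both impregnated devices share rate q: √[p(1−p)/84 + q(1−q)/168].
- At 10/3/3% the variances are 0.09, 0.0291 and 0.0291, with mean 0.0494. The ANOVA value is √(0.0494 × 0.017857) = 0.0297. The true value is √(0.09/84 + 0.0291/168) = 0.0353. The ratio is 0.84.

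Enumerating all 85³ outcomes with exact binomial weights:

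| Rates (%) | SE ratio | ANOVA coverage | Newcombe coverage | ANOVA interval narrower by | ANOVA rejects zero | Newcombe excludes zero |
|---|---|---|---|---|---|---|
| 10/5/5 | 0.90 | 92.0% | 95.8% | 13% | 32.74% | 32.73% |
| 10/3/3 | 0.84 | 90.0% | 95.7% | 19% | 62.24% | 62.23% |
| 10/2/2 | 0.80 | 87.5% | 95.6% | 23% | 78.68% | 78.66% |
| 20/5/5 | 0.83 | 89.5% | 95.5% | 17% | 95.21% | 95.21% |

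As illustrative data, take 8, 3 and 2 infections. The difference is 5/168 − 8/84 = −6.5 points. MSE = 0.0485, SE = 0.0294 and t = 1.970, so the ANOVA interval is −12.3 to −0.7. Newcombe gives −14.9 to −0.6. Both exclude zero; the disagreement is mainly at the far end, on how large the benefit could be.

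**Device-to-device comparisons, if pooled-error t tests were used without adjustment.**
- *Inert impregnated device versus Integra when the other device works.* False positives are 9.3% (10/10/2%), 9.1% (15/15/3%) and 8.6% (20/20/5%), against 4.9–5.1% for a two-proportion test. Requiring a significant F first leaves 8.6–9.1%. Tukey's adjustment gives 4.4%, 4.4% and 4.1%.
- *Ventriclear versus Bactiseal.* The error now goes the other way, because the plain arm's larger variance inflates the standard error. Power is:

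| Rates (%) | Pooled-error t | Two-proportion z | Fisher exact |
|---|---|---|---|
| 15/8/1 | 35% | 62% | 44% |
| 20/8/1 | 27% | 62% | 44% |
| 20/10/2 | 37% | 60% | 47% |

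**The case against.** The strongest case for the plan is that the only test it specifies works. The F test reproduces chi-square, and even with the right contrast added, the ANOVA and the Newcombe interval exclude zero at practically the same rate. With equal rates of 2–20% in all arms the contrast's size is 3.8–5.0%, so it does not exceed nominal. All of this stands. A reader might infer that ANOVA on 0/1 data makes the trial's test invalid, or that every comparison is wrong once catheters differ. The document and the figures do not support that.

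It is also true that the miscalibrated analyses are not in the plan. A reader might infer that the trial will call an inert device different about twice as often as stated. That requires unadjusted pairwise t tests, which Section E does not mention; with Tukey, a usual follow-up to ANOVA, the rate is about 4%. The power loss between the two impregnated devices is smaller against Fisher's test than against the z test. At 10/5/2% it vanishes against Fisher (6.6%, versus 7.3% for ANOVA). That comparison is not the stated goal in any case.

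What the objection does not remove is the need for an estimate. The goal concerns the difference between impregnated and non-impregnated catheters, the plan supplies no way to estimate it for a yes/no outcome, and the one method it names gives an interval that is materially too narrow.

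**Conclusion.** The point holds as a gap in the analysis of infection. It is a should-fix, not a must-fix. The planned F test is sound at this sample size and the yes/no decision on the main comparison is practically unaffected. The interval is the problem: coverage of about 87.5–92% instead of 95% under the four assumed rate patterns, with a width 13–23% short of the Newcombe interval. Unadjusted device-to-device comparisons on the pooled error would also be miscalibrated, but they are not planned.

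The sizes rest on three assumptions: infection counted once per patient as yes/no, 84 patients per arm, and infection rates chosen for illustration. Larger gaps between arms make the shortfall worse; with equal rates it disappears.

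**What to change.** In Section E, limit the single-method sentence and add for infection:
- Analyse it as a proportion per arm, with infection defined as yes/no per patient, using a chi-square or exact test.
- Report the impregnated minus non-impregnated risk difference with a 95% Newcombe or Miettinen-Nurminen score interval.
- Report any device-to-device differences the same way, using only the arms compared, and adjust for multiplicity if pairwise tests are claimed.
- Keep ANOVA, preferably in Welch's form, for duration of placement. The method for cost should be named separately.

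This takes a few sentences and standard software, with no new patients or data. The price is an interval for the main difference about 15–30% wider than ANOVA's, which is the width needed for the stated coverage. If an exact test is chosen for comparing the two impregnated devices, most of the power advantage of the z test is given up, so the choice should be made in advance.
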